measurement of the 6-min walking distance (6MWD). At the same time, it includes the self-measurement of 6min walking distance (6MWD), and patients can complete the self-measurement of 6MWD according to the prompts of the application;

- 6) Implementation and feedback function: It can realize the guidance and adjustment of prehabilitation strategy after reassessment; and set up functions such as daily reminder and prehabilitation activity record.

3.2 To conduct a study on the impact of short-term internet + wearable device-based home-based multilink prehabilitation management on preoperative functional status and prognosis of patients undergoing VATS surgery compared to the traditional model.

A prospective randomized controlled single-blind clinical trial. 64 patients with diagnosed lung occupations intended for VATS surgery were to be included. They were randomized into the “Internet+” group and the traditional prehabilitation control group.

- 1) Sixty-four adults aged ≤ 75 years; suspected lung cancer intended for VATS lobectomy/sublobar resection were selected for the study.
- 2) Prehabilitation intervention: Both groups underwent individualized home-based multimodal prehabilitation strategies, and the timing of the prehabilitation intervention was about 2 weeks from the time the doctor and the patient jointly decided to have the surgery to 1 day before the surgery. The content of prehabilitation included smoking cessation, aerobic training,

anaerobic exercise, nutritional optimization and psychological support. The "Internet+" group used the management mode of online application + wearable devices; the traditional prehabilitation group used the traditional management mode of preoperative preaching + paper records + regular weekly reminders from medical staff.

- 3) Study endpoints: The follow-up period was from the time when the surgeon and the patient decided to operate to 30 days after the operation. The 6MWD was used as the primary assessment of perioperative functional status and the primary endpoint of the study, and patients were evaluated at enrollment, before surgery, and 30 days after surgery. Secondary endpoints included: length of hospitalization, postoperative complications, and pulmonary function, as well as multiple perioperative functional status scores. The feasibility of "Internet Plus" management and patient implementation were assessed.

4. Sample size and statistical methods

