The design of this study was a prospective randomized controlled study, and the sample size of this study was based on the difference in the primary outcome 6-minute walk test distance (6MWD) between the two groups at 30 days postoperatively. It is currently recognized that a difference of 30m in a patient's 6MWD is clinically significant. According to the pre-test of the research team, the standard deviation of the 6MWD was 40 m. The probability of class I error was calculated as 0.05 bilaterally and $\beta=0.2$ to obtain 29 patients in each of the two groups, and 32 patients in each of the two groups were taken to account for the

10% shedding of medical records.

The statistical software for this study was in R language (R Foundation for Statistical Computing, Vienna, Austria; version 3.5.2). Measurements were expressed as mean \pm standard deviation or quartiles, depending on the distribution, and counts were expressed as frequencies. In this study, for the primary outcome 6MWD, as well as for the WHODAS 2.0, and the HADS psychological scores, repeated measurements were taken at different time points in the same patient. Considering the correlation between multiple measurements, a linear mixed-effects model was developed in this study to analyze the effect of the intervention. Intervention factors, time points as categorical variables, and interactions between intervention factors and time as fixed effects were included in the model. When there was no evidence in the model suggesting an interaction between the intervention and time, it was removed from the model to estimate the effect of the intervention on the primary outcome at all time points and the effect of time on the primary outcome. Also, given the potential bias of patients missing visits, we will perform sensitivity analyses of the worst measurements for all patients with missing 6MWD data and determine whether missing data have an impact on the analysis of the primary outcome. For other single-measure secondary outcomes, group comparisons were performed using the paired t test for measures that satisfied normality and the nonparametric Mann-Whitney U test for measures that did not satisfy normality. Count data were expressed as frequencies, and intergroup comparisons were performed using the χ^2 test. The test level was $\alpha=0.05$. A statistically significant difference was defined as a two-sided $P<0.05$.

5. Patient inclusion and exclusion criteria

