[figure not shown]
performed twice a day for 10 minutes each time, and respiratory exercises include balloon blowing, three-ball instrument, respiratory trainer, and active cycle breathing techniques. Individualized protocols are developed based on the patient's underlying respiratory function and tolerance.

v) Dietary and psychological adjustments

The European Society of Clinical Nutrition and Metabolism recommends a daily protein intake of 1.2g/kg-1.5g/kg (ideal weight for obese patients) for surgical patients. Patients are advised to change unhealthy dietary habits, especially high-calorie and high-fat diets, and increase the intake of vegetables, fruits and high-quality proteins (fish, chicken breast and other lean meats, milk, eggs, soybeans) as appropriate. In addition, patients are advised to supplement high-quality protein, such as whey protein powder, one hour before exercise every day to better promote muscle synthesis according to their individual conditions. Encourage patients to perform self-psychological adjustment and listen to relaxing music to sleep before bedtime every day.

The 6MWD at 30 days postoperatively was used as the primary assessment of functional status and the primary endpoint of the study (enrollment, preoperative and 30 d postoperative); secondary endpoints included pulmonary function, length of hospital stay, ICU stay, postoperative complications, and hospitalization costs, and the HADS assessed perioperative psychosocial, the QoR-15 scale assessed

near-term prognosis, and the WHODAS-2.0 scale assessed mid-term prognosis.

7. Research quality control

- 1) All 6-minute walk tests were measured by a unified person, conducted in accordance with international standard procedures and equipped with first-aid

medicines, so that patients could be dealt with in a timely manner if they felt unwell or needed to take a rest;

2) The whey protein powder provided free of charge to the patients was selected from "Nerishi" isolate whey protein powder through the Nutrition Department of the hospital, taking into consideration the purity, purification method, safety, taste and other issues;

3) For patients in the traditional prehabilitation group who have no wearable devices, patients are provided with free finger oxygen meters to facilitate patients to record their heart rate during aerobic exercise, adjust the intensity of exercise, and ensure the safety and effectiveness of exercise;

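### An interaction pre-test decides whether the primary 6MWD result is the 30-day difference the trial was sized for

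*Combined protocol and SAP*

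**What the plan says.** Three places bear on the primary 6MWD analysis.

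- **Section 4, sample size.** The trial is sized on the 6MWD difference "between the two groups at 30 days postoperatively": 30 m, SD 40 m, two-sided 0.05, beta 0.2, giving 29 per group and 32 after dropout.
- **Section 6, endpoint paragraph.** "The 6MWD at 30 days postoperatively was used as the primary assessment of functional status and the primary endpoint of the study", followed by a parenthesis listing the three assessments.
- **Section 3.2, item 3.** "The 6MWD was used as the primary assessment of perioperative functional status and the primary endpoint of the study". No single time point is named, and "patients were evaluated at enrollment, before surgery, and 30 days after surgery".

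The analysis text in Section 4 fits group, categorical time and their interaction. The condition for dropping the interaction is worded as "When there was no evidence in the model suggesting an interaction between the intervention and time". The consequence for the term is that "it was removed from the model to estimate the effect of the intervention on the primary outcome at all time points". The text sets no threshold for this step. The only test level given is general: "A statistically significant difference was defined as a two-sided" P below 0.05. It does not say which contrast is reported if the interaction stays, or whether enrollment 6MWD is an outcome or a covariate.

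**The concern.** Once the interaction is removed, the model has a single group coefficient shared by all modelled visits and cannot give a separate 30-day difference. The data then choose what the primary result estimates. Not finding an interaction in a trial of this size does not show that the effect is constant.

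What is averaged is also open. There are two readings.

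- **Three-visit reading.** All listed visits are outcomes and there is no baseline covariate. The pooled effect then includes enrollment, where randomization makes the expected difference zero. Any real later effect is itself an interaction, so removal dilutes the result.
- **Two-visit reading.** Only the pre-surgery and 30-day visits are modelled. The pooled effect is their average, which can be too low or too high for day 30.

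An overstatement is possible because the intervention runs "from the time the doctor and the patient jointly decided to have the surgery to 1 day before the surgery" (Section 3.2, item 2), so an early benefit could fade by day 30.

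**Working it through.** **Inputs from Section 4.** SD 40 m, target difference 30 m, 29 per arm, two-sided 0.05.

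**Assumptions not in the documents.** Compound symmetry with correlation rho of 0.5, 0.6, 0.7 or 0.85; complete data; the general 0.05 level applied to the interaction test; the 30-day contrast reported when the term is kept; and the visit-specific effects, written enrollment / pre-surgery / day 30.

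**1. The plan's own figure.** The SE of the 30-day difference is 40 × √(2/29) = 10.5 m, and 30/10.5 = 2.86. With 56 df the noncentral t power is 80.1% at 29 per arm (78.7% at 28). 29 × 1.1 = 31.9, so 32 per group. The sizing reproduces for a 30-day contrast.

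**2. What the pooled effect estimates.**

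- Three visits: 0/15/30 gives (0 + 15 + 30)/3 = 15 m, and 0/30/30 gives 20 m, each for a true 30 m at day 30.
- Two visits: 30 m before surgery and 15 m at day 30 give (30 + 15)/2 = 22.5 m for a true 15 m.

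**3. How often the term is removed.** The interaction F test has noncentrality λ = (29/2) × Σ(effect − mean effect)² / [40² × (1 − rho)]. For 0/15/30 over three visits the sum is 225 + 0 + 225 = 450. At rho 0.5, λ = 14.5 × 450/800 = 8.16 on 2 and 112 df, and the test misses the interaction in 29% of trials. For effects 15 m apart over two visits the sum is 112.5 and λ = 14.5 × 112.5/800 = 2.04 on 1 and 56 df, so it is missed in 71%.

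**4. The whole procedure.** I used 100,000 simulated trials per scenario and rho, reporting the pooled effect if the interaction P is 0.05 or more and the 30-day contrast otherwise. Monte Carlo error is at most about 0.16 percentage points. Entries are for rho 0.5 / 0.6 / 0.7 / 0.85.

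| Reading and true effects (m) | Term removed, % | Significant, % | Fixed 30-day test, % |
|---|---|---|---|
| Three visits, 0/15/30 | 29 / 19 / 9 / 0.2 | 74 / 76 / 78 / 80 | 80 |
| Three visits, 0/30/30 | 16 / 9 / 3 / 0 | 80 | 80 |
| Two visits, 0/15/30 | 71 / 65 / 56 / 27 | 76 / 75 / 75 / 77 | 80 |
| Two visits, 0/30/15 | 71 / 65 / 56 / 27 | 52 / 48 / 43 / 34 | 29 |
| Two visits, 0/30/30 | about 95 | 89 / 87 / 85 / 83 | 80 |

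For three visits and 0/15/30, the mean reported effect over all trials is 27.4 / 28.4 / 29.3 / 30.0 m, and the confidence interval covers the true 30 m in 85 / 89 / 93 / 95% of trials.

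Rejection rate when the true 30-day difference is zero (nominal 5%):

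| True effects (m) | Three visits, % | Two visits, % |
|---|---|---|
| 0/15/0 | 8.5 / 7.9 / 7.1 / 5.7 | 11.1 / 10.1 / 9.2 / 6.6 |
| 0/30/0 | 7.7 / 6.4 / 5.4 / 4.9 | 10.8 / 8.0 / 6.1 / 5.1 |
| 0/0/0 | 5.4 / 5.5 / 5.4 / 5.1 | 5.8 / 5.4 / 5.5 / 5.1 |

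**5. How much of the shift is due to the rule.** Trials in which the term is removed are a selected group. For three visits and 0/15/30 (rho 0.5 / 0.6 / 0.7) they report 15 m on average, while their own observed 30-day difference averages 24 / 24 / 23 m. The rule itself lowers the estimate by 9.1 / 8.6 / 7.9 m, not by 15 m. For two visits and 0/30/15 their observed 30-day difference is about 17.5 to 18.4 m, so the rule adds about 4 to 5 m, not 7.5 m.

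**6. Precision.** SE = 10.5 m times the factor shown, for the same four rho values.

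| Estimate | Factor | SE, m |
|---|---|---|
| 30-day contrast, unadjusted | 1 | 10.5 |
| Pooled, three visits | √((1 + 2rho)/3) | 8.6 / 9.0 / 9.4 / 10.0 |
| Pooled, two visits | √((1 + rho)/2) | 9.1 / 9.4 / 9.7 / 10.1 |
| 30-day contrast, adjusted for enrollment 6MWD | √(1 − rho²) | 9.1 / 8.4 / 7.5 / 5.5 |

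**The case against.** The strongest reply is that a perioperative average was intended. Section 3.2 names 6MWD as primary with three visits and no single time point, and the Section 6 sentence carries all three visits in its parenthesis. This is possible, but it does not rescue the plan. The subject of the Section 6 sentence is 6MWD at 30 days, the parenthesis reads as the assessment schedule, and the sample size rests on the 30-day difference. An intended average would contradict both.

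A second reply is that under a constant effect the common coefficient is also the 30-day effect, so the pre-test only selects an estimator. That holds for the two-visit reading with equal later effects, where pooling is unbiased and gains power. It fails if enrollment is a modelled outcome.

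Third, the larger figures come from the two-visit reading, which has less support in the text, and from a threshold the plan does not state. Both points stand as limits on size. A looser threshold helps: for three visits and 0/15/30 with rho 0.5 to 0.7, power is 77% to 79% at 0.10 and 79% to 80% at 0.20. For two visits and 0/30/15 at rho 0.5, the share of significant trials falls from 52% to 46% and 40%.

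Fourth, comparing an adjusted 30-day SE with an unadjusted pooled SE is not like for like. If both are adjusted under the two-visit reading, the pooled factor is √((1 + rho)/2 − rho²), giving 7.4 / 7.0 / 6.3 / 4.7 m. Pooling then keeps an SE about 15% to 18% smaller. That is the price of estimating the 30-day difference.

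**Conclusion.** The concern holds. As written, a pre-test without a stated threshold decides whether the primary result is the 30-day difference, and no part of the plan fixes that contrast.

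The average harm is modest and depends on the assumed correlation, threshold and effect pattern. Under the three-visit reading power falls by at most about 6 points in the scenarios tabulated, and for 0/15/30 the problem almost vanishes at rho 0.85. Rejection is about 5% to 6% when there is no effect at any visit. It reaches 8.5% (three visits) or 11.1% (two visits) when a pre-surgery effect exists and the 30-day effect is zero. Three-visit pooling under 0/30/15 and two-visit pooling under equal later effects cause no bias. The sample size is not in error. The defect is in the analysis rule and should be corrected.

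**What to change.** In Section 4, for 6MWD:

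- delete the sentence that removes the interaction, and keep the term whatever its P value;
- name the model-based group contrast in 6MWD at 30 days as the single primary test, two-sided 0.05;
- state how enrollment 6MWD enters, either as a covariate or as an outcome with a common mean in both arms;
- report the pre-surgery contrast as secondary.

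Align Section 3.2, item 3 with this. If the sponsor did intend an average over visits, the plan must say so, define which visits are averaged, and revise the sample size basis and the Section 6 endpoint. The removal sentence names only the primary outcome; if it is also meant for WHODAS 2.0 and HADS, treat them the same way.

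**Cost.** Two or three sentences, with no extra data or patients. The unadjusted 30-day contrast has a wider interval than the pooled effect, and the power gain from pooling when the two later effects are equal (83% to 89% against 80%, two visits) is given up. Keeping the interaction alone gives the planned 80% power at 29 per arm. Adjusting for enrollment 6MWD is a separate gain. Compared with the unadjusted pooled effect of the current plan, it more than makes up the lost precision at rho 0.6 or above and largely does so at 0.5.

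### The only check on missing 6MWD fills an undefined 'worst' value; if that is a lowest value, the result moves largely with how the losses split between arms

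*Combined protocol and SAP*

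**What the plan says.** Section 4 gives the motive for the check ("given the potential bias of patients missing visits"), the method ("we will perform sensitivity analyses of the worst measurements for all patients with missing 6MWD data") and the purpose, which is to "determine whether missing data have an impact on the analysis of the primary outcome". No other analysis of missing 6MWD appears in the document. The section does not define the worst value, name the visit to be filled, say which model is refitted, or say how large a change would count as an impact.

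Several meanings are open because 6MWD is measured three times: section 3.2 states that "patients were evaluated at enrollment, before surgery, and 30 days after surgery". The end of section 6 fixes the time point of interest: "The 6MWD at 30 days postoperatively was used as the primary assessment of functional status and the primary endpoint of the study". The primary analysis in section 4 is a mixed model with group, visit and their interaction. If there is no evidence of an interaction, "it was removed from the model to estimate the effect of the intervention on the primary outcome at all time points". The sample size allows for "10% shedding of medical records".

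**The concern.** At least three fills fit the text: the lowest value seen in the trial, the lowest value seen in the patient's arm, and the patient's own lower earlier value. They behave very differently.

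Under the first two, every missing patient receives a value far below the mean, whatever the reason for the loss. The arm that loses more patients is pulled down more. If control loses more, the check moves towards Internet+; if Internet+ loses more, it moves away. Agreement or disagreement with the primary result may therefore say as much about the counts lost as about bias. Under the third reading the fill is close to an ordinary value, so little is being stressed.

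At stake is the answer to the question the plan sets itself. The check can raise an alarm when loss is harmless, and it can stay quiet when loss is harmful.

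**Working it through.** **Inputs.** From section 4: target difference 30 m, SD 40 m, two-sided 0.05, power 80%, 29 per arm raised to 32, loss 10%. Assumed: 6 of 64 missing at 30 days (64 × 0.10 = 6.4), normal data, and a 30-day t test in place of the mixed model.

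**The plan's own figure.** The normal approximation gives n = 2 × (1.96 + 0.84)² × 40² / 30² = 27.9, so 28. The t test gives 28.9, so 29, with power 80.1%. Then 29 × 1.1 = 31.9, so 32. The stated figures reproduce.

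**How the split acts.** Let *a* Internet+ and *b* control patients be missing at random, with no true effect and each filled value *D* below the mean. The estimate moves by D × (b − a) / 32.
- Trial-wide lowest: the minimum of 58 values lies about 2.3 SD down, so D = 92 m. At 1 v 5 the shift is 92 × 4 / 32 = 11.5 m.
- Arm's lowest: the minimum of 29 values lies about 2.03 SD down, so D = 81 m. At 1 v 5 the shift is 81 × 4 / 32 = 10.1 m. Each arm gets its own minimum here, so the fill is not common to both arms when there is a true effect.

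**Simulation** (40,000 trials per split; random loss; figures are trial-wide / arm's lowest; split chances hypergeometric):

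| Internet+ v control missing | Chance | No effect: shift (m) | True 30 m: filled estimate (m) |
|---|---|---|---|
| 1 v 5 | 8.6% | +11.5 / +10.0 | 39.4 / 40.0 |
| 3 v 3 | 33% | 0 / 0 | 27.2 / 30.0 |
| 5 v 1 | 8.6% | −11.5 / −9.9 | 14.8 / 20.1 |

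Splits of 2 v 4 and 4 v 2 have a 24% chance each, so the arms differ by two or more in about 67% of trials. At 5 v 1 with a true 30 m, 81% / 47% of significant complete-case Internet+ results are lost.

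**Change of conclusion, averaged over splits.** With a true 30 m and random loss, it changes in about 25% / 15% of trials. Imbalance is not the whole cause: at exactly 3 v 3 it still changes in about 16% to 18% / 6% to 7% across repeat runs. There the cause is added variance and, for the trial-wide fill, shrinkage: 29 × 30 / 32 = 27.2 m. With no effect the averaged figure is 5.5% / 5.7%.

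**Loss related to the outcome** (no effect; assumed log-weight of 1.5 per SD of the 30-day value; 20,000 trials):
- Both arms lose poor walkers: mean absolute error falls from 3.8 m to 2.7 / 2.9 m.
- Only Internet+ loses poor walkers: mean bias is +6.4 m and the check moves −6.5 / −3.8 m, the right direction.
- Internet+ loses poor walkers and control loses good ones: mean bias is +9.7 m and the check moves only −0.9 / +0.6 m.

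**Own earlier value** (assumed correlation 0.7; 1 v 5; no effect): the shift is +1.5 m if distance does not fall by day 30, and −2.2 m if it falls by 30 m.

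**Mixed model** (250 trials; random intercept; 1 v 5; no effect): the 30-day contrast moves +11.5 / +9.8 m with the interaction kept. With it dropped, the all-visit effect moves +3.8 / +3.3 m, about a third as much, since one visit of three is filled.

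**The case against.** The strongest reply is that following the split and detecting bias are not alternatives. When both arms lose poor walkers, the arm losing more is the one flattered by its remaining patients. In that setting the check's movement correlates about 0.8 / 0.7 with the actual error and points the right way in 81% / 77% of trials. If only Internet+ loses poor walkers, false Internet+ wins fall from 9.7% to 2.6% / 6.0%. For a walking test after lung resection, loss of poor walkers is a natural worry. This stands, and it rules out a reading that the check is worthless. The failure with opposite kinds of loss is an assumed scenario that nothing in the documents suggests.

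A second reply is that the alarm rates come from a 30-day t test, while the plan uses a three-visit model. That stands as a limit: the mixed model was tried at one split only, and dropping the interaction cuts the shift to 3 to 4 m. With the interaction kept, the 30-day shift is essentially the same.

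A third reply is that a shift grid also overturns results under random loss, and that multiple imputation from earlier 6MWD largely repeats the mixed model. Both are true. The gain is that the grid shows how large a departure is needed, by arm, instead of making one jump whose size and direction depend on the counts lost.

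A reader might also infer that the check was meant as a conservative bound and fails as one, that the trial's error rate is inflated, or that the different contact schedules in section 7 will make losses unequal. The plan never calls the check conservative. The check does not alter the primary mixed-model estimate or its error rate. Unequal loss is plausible, but the documents do not show it.

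**Conclusion.** The concern holds in a limited form. The plan's only missing-6MWD check is undefined, and the possible definitions give different answers. Under a lowest-value fill it moves a null 30-day difference by about 10 to 11.5 m at 1 v 5, against a 30 m target. Under random loss with a true 30 m it changes the conclusion in about 25% / 15% of trials, only partly because of imbalance. It is useful if poor walkers are lost in both arms or in Internet+ only, and it can miss bias if the arms lose different kinds of patient. Under the patient's own earlier value the split argument does not apply; the weakness there is mildness.

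These sizes rest on 6 of 64 missing, normal data with SD 40 m, and the t-test stand-in. The outcome-related results also rest on the assumed strength of selection. The reliability of the sensitivity analysis is in question, not the primary estimate. The plan should be changed before the data are analysed.

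**What to change.** Make the main sensitivity analysis a multiple imputation of 30-day 6MWD under missing-at-random, using group, enrolment 6MWD and pre-operative 6MWD. Then shift the imputed values separately in each arm over a prespecified grid, for example −60 to +60 m (illustrative, not from the documents). Include Internet+ lowered with control raised, and the reverse. Report the combinations at which the two-sided 30-day conclusion changes, as tipping points and not as a pass or fail.

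Both arms must vary. Lowering Internet+ alone by 60 m moves the estimate 60 × 1 / 32 = 1.9 m at 1 v 5 but 60 × 5 / 32 = 9.4 m at 5 v 1. Opposite 60 m shifts move it 60 × 6 / 32 = 11.25 m at any split.

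Keep the worst-value run as a descriptive extra, stating what worst means, which visit is filled and which model is refitted. Report missing 6MWD and reasons by arm and visit.

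The cost is a short R script and one small table, using 6MWD already scheduled. The grid range must be chosen in advance and its corners are harsh: with a true 30 m and random loss, opposite 30 m shifts overturn 21% to 25% of significant missing-at-random results, and opposite 60 m shifts 53% to 57%.

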5.1 Inclusion

- 1) Age: 18-75 years;
- 2) 64 adults with suspected lung cancer proposed for VATS lobectomy/sublobar resection.

5.2 exclusion:

- 1) Patient refusal;
- 2) ASA classification III or higher;
- 3) Pre-neoadjuvant chemotherapy;
- 4) Inability to cooperate (psychiatric abnormalities, impaired consciousness, mental retardation);
- 5) Comorbidities cannot tolerate home rehabilitation or functional motor examination;
- 6) Inability to use a smartphone or read Chinese;
- 7) Average weekly moderate-intensity/high-intensity exercise of >90min/>60min.

6. Research process

- 1) Patients were assessed for enrollment criteria at the time of their initial outpatient visit and decision to proceed with surgery. After obtaining informed consent from the patients, basic information (basic, past medical history, metabolic equivalents, etc.), smoking status, ASA classification, metabolic equivalents, 6MWD, lung function, grip strength, NRS 2002 nutritional risk screening, HADS and WHODAS 2.0 scores were collected
- 2) Both groups were given routine preoperative anesthesia clinic visits and

guidance, and a short-term home multimodal prehabilitation intervention strategy of about 2 weeks, including smoking cessation, aerobic exercise, impedance training, respiratory exercise, nutritional guidance, whey protein powder supplementation and psychological support. Elastic bands, whey protein powder and respiratory trainers were distributed to patients in both groups.

The “Internet+” team trained patients on the online application of the “Preoperative Family Prehabilitation Program” . The patients used the online application for prehabilitation, followed the exercises, and used the sports bracelet as a wearable device to adjust the exercise intensity and record the exercise time.

Patients in the traditional group were issued a portable finger oxygenator to assist in the completion of exercises, as well as a Pre-Rehabilitation Manual and Completion Record Form, which patients were instructed to fill out daily, and patients were followed up twice a week.

Comprehensive reference to previous studies and prior research by the group, combined with patient execution, to propose a concise and easy-to-follow exercise program:

- i) Tobacco and alcohol cessation
- ii) Aerobic exercise

Aerobic exercise is the core of exercise training in a way that consists of two steps, the first step being a 5-minute warm-up process. The second

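### A paired t test is specified for comparing two independent randomised groups on normally distributed single-measure secondary outcomes

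*Combined protocol and SAP*

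**What the plan says.** Section 3.2 describes a prospective randomised trial in which 64 patients are allocated to an Internet+ "group and the traditional prehabilitation control group".

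Section 4 sets three analysis rules:

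- 6MWD, WHODAS 2.0 and HADS, measured repeatedly in each patient, go to a linear mixed-effects model.
- For the remaining continuous outcomes: "For other single-measure secondary outcomes, group comparisons were performed using the paired t test for measures that satisfied normality". Where normality fails, the same sentence prescribes "the nonparametric Mann-Whitney U test for measures that did not satisfy normality".
- For categorical data: "Count data were expressed as frequencies, and intergroup comparisons were performed" with a chi-square test.

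The sample size in section 4 uses a 30 m difference, an SD of 40 m, two-sided 0.05 and beta 0.2 "to obtain 29 patients in each of the two groups", raised to 32 per group for 10% loss.

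Section 6 names the outcomes from which the single-measure set must come: "secondary endpoints included pulmonary function, length of hospital stay, ICU stay, postoperative complications, and hospitalization costs", with QoR-15 also listed there.

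**The concern.** A paired t test analyses within-pair differences, so each value in one group must have a designated partner in the other. Nothing in the documents creates such partners.

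The sentence cannot be read as a within-patient comparison either. It concerns comparisons between groups on outcomes measured once, and one value per patient leaves nothing to pair within a patient.

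If the rule is followed literally, one of two things happens. With unequal groups, the test cannot use everyone: it either fails or is run on a subset, which could discard observed patients. With equal groups, it runs, but the p-value and confidence interval depend on the order in which patients happen to be listed, so another analyst with the same data could reach a different verdict.

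**Working it through.** **1. Does the rest of the plan assume independent groups?**

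- Mann-Whitney U, the non-normal alternative in the same sentence, is an independent-samples test. The paired counterpart would be the Wilcoxon signed-rank test.
- The chi-square test between groups also assumes independence.
- Sample size, inputs from section 4: d = 30/40 = 0.75, two-sided alpha 0.05, power 0.80. The normal approximation 2(1.96 + 0.84)²/0.75² gives 27.9, so 28. The exact independent two-sample t calculation gives 28.90, so 29, which is the plan's figure. Then 29 × 1.10 = 31.9, so 32, also the plan's figure.

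Every other element treats the groups as independent.

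**2. Equal groups, no loss (n = 32 each)**

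- Independent: t = (mean difference) / √[(s₁² + s₂²)/n], df = 62, critical value 1.999.
- Paired: t = (mean difference) / √[(s₁² + s₂² − 2s₁₂)/n], df = 31, critical value 2.040.

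The two differ in the degrees of freedom and in s₁₂, the sample covariance across the listed rows. With unlinked patients s₁₂ has expectation zero, but its realised value depends on row order.

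At an illustrative d = 0.75 the noncentrality is 0.75 × √(32/2) = 3.0 for both tests. Power is 84.0% independent and 82.8% paired, a cost of 1.2 points.

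**3. Dependence on row order**

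For each target p, 20 simulated normal data sets of 32 per group were scaled to give exactly that independent-test p. Each was randomly re-paired 10,000 times.

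| Independent p | Share of pairings with paired p<0.05 |
|---|---|
| 0.01 | 100% |
| 0.03 | 85% |
| 0.05 | 42% |
| 0.07 | 16% |
| 0.10 | 3% |
| 0.20 | about 0.01% |

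At independent p = 0.05, the central 95% of paired p-values runs from 0.019 to 0.095.

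**4. How likely are unequal groups?**

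If each of 32 patients per group is lost independently with probability q, P(unequal) = 1 − Σ P(K = k)², with K ~ Binomial(32, q).

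| Loss q | P(unequal) |
|---|---|
| 1% | 42% |
| 2% | 60% |
| 5% | 76% |
| 10% (the plan's rate) | 83% |
| 15% | 86% |

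**5. What a forced paired test could cost**

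This used 40,000 simulated trials at each of d = 0 and d = 0.75, with 32 per group and 10% independent loss. The two paired variants are possible workarounds; the plan describes neither.

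| Analysis | Mean pairs | Power at d = 0.75 |
|---|---|---|
| Independent t, all observed patients | not applicable | 79.9% |
| Paired, cut to the smaller group | 27.9 | 77.0% |
| Paired by row index, incomplete rows dropped | 25.9 | 73.7% |

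The last row follows from 32 × 0.9 × 0.9 = 25.9 pairs, so about 52 of the 64 × 0.9 = 57.6 observed patients are used. Type I error is 5.0% to 5.2% in all three.

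**The case against.** The best defence is that this is a naming slip. The wording is about comparing groups, the companion tests are for independent samples, and the English shows other signs of translation. That is plausible. But this sentence is the only specification for these outcomes and nothing corrects it, so an analyst must either follow a test that does not fit or depart from the plan.

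Four points on size have merit:

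- **Unequal groups may expose the slip.** Software may stop with an error rather than silently drop patients. The losses in step 5 are therefore what could happen, not what must.
- **The 10% loss rate belongs to 6MWD at 30 days.** Length of stay, ICU stay and costs are recorded in hospital, where loss may be lower. At 1% to 2% loss the chance of unequal groups is 42% to 60%, which is still substantial.
- **Few outcomes may be affected.** Stay and cost data may well fail normality and go to Mann-Whitney. Lung function is also collected at enrolment ("6MWD, lung function, grip strength, NRS 2002 nutritional risk screening"), so it may not count as single-measure. QoR-15 is a plausible candidate, but the plan does not assign it to this rule.
- **Verdicts seldom change.** In a simulation with 32 per group and no loss, paired and independent verdicts differed in 1.6% of null trials, 5.8% at d = 0.5 and 3.6% at d = 0.75.

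These points limit the consequence. None makes the paired test appropriate.

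**Conclusion.** The concern holds: the named test does not match the design and conflicts with the alternative given in its own sentence. Its reach is confined to continuous, single-measure secondary outcomes judged normal, and the primary conclusion is not threatened.

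False positives are not the issue, provided row order is unrelated to outcome. The harm is a result that is undefined with unequal groups, or that depends on row order with equal ones. The latter matters only for independent-test p-values of roughly 0.02 to 0.10, and little at the ends of that range. The power cost at d = 0.75 is 1.2 points with complete data. At 10% loss it could be 79.9 − 77.0 = 2.9 to 79.9 − 73.7 = 6.2 points under the two workarounds.

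These sizes rest on normal data, independent losses, the plan's 10% rate and an effect of 0.75 SD borrowed from 6MWD. The error itself rests on none of them. It should be fixed before analysis.

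**What to change.** In section 4, replace the paired t test with an independent two-sample t test, state in advance whether it is Welch or pooled, and report the mean difference with its 95% CI. Keep Mann-Whitney U for non-normal outcomes.

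This is a change of one phrase. It needs no extra patients or data, and the 29 and 32 per group stand because they already come from an independent-groups calculation.
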